pregnancy, either remotely or in-person, similar to those in the AME group. In-person visits may occur at the hospital/clinics or another private mutually-agreed upon location; remote visits will be via a secure remote platform, such as the University's HIPAA-compliant Zoom. Visits will be approximately 10 minutes, similar to the intervention group. In this time, participants will view a standard set of web-based videos addressing evidence-based infant care, unrelated to feeding/breastfeeding. Videos will focus on a different theme each week (e.g., safe sleep, car seat safety, managing crying/colic), downloaded from free and reputable patient education sites. If visit is remote, study staff will attempt to "screen share" videos so that we may verify that participant actually views/receives the intended education (rather than directing participant to view videos on their own). Data Collection and Procedures Unrelated to Intervention Delivery: We will collect EMR data regarding maternal pre-pregnancy body mass index (BMI) and gestational weight gain, maternal and infant health conditions, labor and delivery information, and hospital infant feeding practices from the antenatal and postpartum medical records. Prenatal, intrapartum, and postpartum EMR data is housed within the hospital data systems, which the study team will access via their research and clinical affiliation with the hospital after IRB approval. In the postpartum period, study measures (surveys) assessing breastfeeding practices, perceptions, problems, satisfaction, plans, and education/support, as well as maternal mood, birth experience, childcare plans and use, and maternal employment (see questionnaires), will be completed by participants in both groups at weeks 2, 6, and 12 weeks, and 6 and 12 months postpartum. These measures may be completed remotely via emailed survey, in recognition of the time constraints faced by new mothers in scheduling study visits and calls. When difficulties are encountered in electronic survey completion, we will call participants or, when feasible, meet them during regularly scheduled postpartum clinic visits to complete measures (or at another mutually agreed upon time/location). If a participant elects to complete postpartum measurements and collection of a milk sample, the survey may be completed in-person at that time, as well. A subset of participants will also have included into their Baseline and postpartum surveys questions on sexual dysfunction. Please note that this survey is necessarily concurrent with a specific timepoint, and so participants who have already completed their participation in the study will not be asked to retrospectively complete this survey. In fulfillment of Aim 3, we will conduct individual telephone interviews with $\approx 25\%$ of participants from both groups at 6 weeks postpartum, or earlier if they indicate that they discontinued breastfeeding at the 2 week postpartum survey or otherwise notify us at any point that they have decided to not start breastfeeding, do not initiate breastfeeding, or stop breastfeeding. We anticipate conducting interviews with approximately 70 participants, 35 from each group, selected purposively based on variability in AME uptake (e.g., some participants who did not complete any AME, some who did it once daily, twice daily, etc.), demographics, and current breastfeeding status to achieve a representative group). Interviews will continue until thematic saturation is reached (estimated at ≈25% of sample from our prior research). Interviews will address aspects of both AME and the control condition to maintain participant blinding to study purpose. Specifically, we will query participants on motivating factors for study participation; perceived benefits/utility of AME and antenatal video-based infant education; experiences with and evaluation of other breastfeeding and infant education support resources; experienced or anticipated burdens/challenges/drawbacks to AME and the control condition; and for AME participants, factors/contexts impacting AME uptake and use of antenatal-expressed milk, as well as suggested modifications to the AME intervention or study protocol. Interviews will be conducted by a qualitative research consultant or study personnel. Interviews will follow a semi-structured interview guide, adapted from our current AME pilot RCT, and may be modified as the study progresses based on themes raised in prior interviews or issues encountered by study personnel. Interviews are expected to last 30-45 minutes and will be audio-recorded and transcribed verbatim by QDAP, another secure (e.g., HIPAA compliant) transcription service, or study personnel. Both audio files and transcripts will be retained electronically without identifying information in accordance with IRB protocols.

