
STATISTICAL DESIGN AND POWER

Sample Size and Power

The total proposed enrollment of 280 women was determined considering a feasible rate of recruitment, expected effect size of the AME intervention on primary outcomes, testing of multiple hypotheses, and anticipated rate of attrition and protocol non-adherence at 2 weeks postpartum (primary outcome assessment). Our recent intervention research with normal weight and overweight/obese women demonstrates medium sized effects (standardized mean difference, d) for the AME intervention at 1-2 weeks postpartum compared to an education control in terms of higher levels of breastfeeding selfefficacy (AME: M=52.59, SD=9.92, Education: M=45.71, SD=15.71, d=0.53) and greater percentage of breast milk feeds (AME: M=89.50, SD=20.372; Education M=78.64, SD=27.303, d=0.45). Regarding exclusive breastfeeding at 1-2 weeks, rates of 0.27 have been reported among overweight/obese women.32 With a sample size of at least 210 (105 per group), we can detect with .80 power betweengroup differences in the proportions in breastfeeding exclusivity at 2 weeks postpartum as small as .172 (medium effect size of OR=2.55 using likelihood ratio chi-square statistics) at an adjusted test-wise significance level of .0167. While there is a fair amount of heterogeneity in the published effect sizes for breastfeeding support interventions among overweight and obese women and for AME specifically, our estimate lies in the range of reported effect sizes in the field. 12,32 While the examination of long-term efficacy of AME is more exploratory (Aim 2), we will be able to detect small to medium interaction effects between groups over time as small as f = .323 when using repeated measures F-tests with at least four postpartum outcome time points. Our pilot work and previous studies utilizing similar populations and recruitment sites indicate that we can conservatively anticipate combined study attrition and intervention dropout at ≈25%. To ensure 210 participants with complete follow-up to 2 weeks and no protocol deviations, we will enroll 280 women.

Statistical Methods

Preliminary Analyses: For Aims 1 and 2, detailed exploratory data analyses will first be performed, involving data description and data screening for anomalies (e.g., outliers, nonnormality, etc.). The results from this initial investigation will be used to: 1) describe

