univariate and bivariate data distributions; 2) identify imbalances between treatment groups and associations between the dependent variables and suspected covariates/confounders; 3) evaluate the amount and patterns of missing data; and 4) check for violations of statistical assumptions for the planned analyses. If statistical assumptions are seriously violated, data transformations or more statistically robust methods will be considered. Covariates/confounders will be included in models secondarily, and their impact on the effect of the primary independent variable on the study outcomes will be evaluated. The randomness of missing data will be investigated using available information on subject characteristics to help discern patterns in the missing data, identify the possible covert missing data mechanisms, and inform the choice of the strategies to handle missing data. We will conduct logistic regression models to compare the characteristics of participants who remained in the study versus those who dropped out to determine if data are missing at random. If data are ignorably missing (i.e., not related to the outcome itself), likelihood estimation procedures, such as those in SAS PROC MIXED, GLIMMIX and NLMIXED as well as Mplus, will produce unbiased estimates while allowing us to retain cases with missing values on the outcome variables. If needed, multiple imputation would be used to impute missing values on the predictor variables. If data are not ignorably missing (i.e., non-randomly missing), we may use pattern mixture modeling to account for informative attrition.

Analysis Strategies for Aims 1 and 2: To examine the efficacy of the remotely-delivered AME intervention relative to the attention control on breastfeeding outcomes during hospitalization to the first two weeks postpartum (short-term; Aim 1) and up to the first 12 months (long-term; Aim 2) among overweight and obese (BMI \geq 25) women, an intent-to-treat (ITT) approach will be used, where all participants will be included in analyses as randomized, regardless of protocol adherence/deviations, treatment received, or withdrawal. Adherence to the assigned intervention, however, will be monitored, and the sensitivity of the results under the ITT model will be explored to identify the effects of the amount of intervention received (e.g., number of AME study visits) and deviations in protocol on outcomes.

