distribution will be considered with an identity link to the linear predictors. Random effects for participants will also be included. Fixed and/or time-dependent covariates (e.g., pre-pregnancy BMI category [25.0-29.9; 3034.9; 35-39.9; 40+]) may be included secondarily to adjust for group imbalances or variables related to the dependent variables based on the literature or data screening results. Standard fit criteria (e.g., AIC and BIC) also will be used to identify the best-fitting repeated measures covariance structure. F-tests will test the main and interaction effects included in the model. Individual regression parameters will be estimated with confidence intervals. For each model, residual analyses will be conducted to identify sources of model misspecification, outliers, and influential observations. Sensitivity analyses will be performed to discern the impact of influential cases on modeling results. Linear contrasts will be specified in the repeated measures models to test whether the AME intervention demonstrates greater improvements in breastfeeding outcomes compared to the attention control at each time point, in particular, when conducting hypothesis testing on the primary short-term outcomes. Point and interval estimates will be obtained for each of the comparisons examined.

For event history type outcomes (e.g., breastfeeding duration, days to the onset of lactogenesis II, days to any formula) Cox proportional hazards regression methods will be applied to allow for possible censoring of the event of interest and inclusion of the fixed and time-dependent predictors. For summary outcomes (e.g., proportion of breast milk in-hospital), generalized linear modeling will be applied.

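### Women who answer no postpartum survey drop out of the 2-week models despite the intention-to-treat statement, and the in-hospital feeding record that could partly stand in for them is not used there

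*Combined protocol and SAP*

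**What the plan says.** - **Analysis set** (Analysis Strategies for Aims 1 and 2): "all participants will be included in analyses as randomized, regardless of protocol adherence/deviations, treatment received, or withdrawal".
- **Primary outcomes and model** (same section): the three primary outcomes at 2 weeks are exclusive breast milk feeding, percentage of feedings that were breast milk, and breastfeeding self-efficacy. Repeatedly assessed outcomes go into generalized linear mixed models with group, time, their interaction and participant random effects. The 2-week hypotheses are tested by linear contrasts in those models.
- **When outcomes are measured** (Data Collection and Procedures Unrelated to Intervention Delivery): surveys at 2, 6 and 12 weeks and at 6 and 12 months. The same section collects from the medical record "hospital infant feeding practices from the antenatal and postpartum medical records".
- **Use of the hospital record** (end of the modelling text): "For summary outcomes (e.g., proportion of breast milk in-hospital), generalized linear modeling will be applied".
- **Missing data** (Preliminary Analyses): missing outcomes are left to likelihood estimation if loss is ignorable, and "multiple imputation would be used to impute missing values on the predictor variables" if needed. Dropouts are compared with completers by logistic regression. Pattern mixture modelling may be used if loss is not ignorable.

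**The concern.** The feeding outcomes have no value before birth, and the first survey occasion is week 2. Likelihood estimation keeps a woman who has at least one observed outcome and cannot keep one who has none. With imputation confined to predictors, nothing brings her back, so the set analysed for the primary outcomes is smaller than the one promised.

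The plan's statement that likelihood methods are unbiased under ignorable loss is true only given the data in the model. Suppose mothers whose infants had formula in hospital answer less often. Loss could then be ignorable given the hospital record, yet not ignorable in a model that omits it. At stake are the 2-week exclusivity and percentage contrasts, where bias could arise that data already being collected would reduce.

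**Working it through.** **The plan's own figures.** Sample Size and Power gives 210 evaluable women and about 25% combined attrition and intervention dropout: 210 / (1 - 0.25) = 280, which reproduces. If the whole 25% were survey loss, 0.25 x 280 = 70 women, about 35 per arm, would lack 2-week data. The split is not stated, so the number with no survey at all lies between 0 and about 70.

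The plan takes a reference rate from the literature ("rates of 0.27 have been reported among overweight/obese women"). With 105 per group, two-sided alpha .0167 and power .80, 105 per group reproduces for .27 v .485 (OR 2.55, a rise of .215). A rise of .172 from .27 goes to .442, which is OR 2.14. These two alternatives differ. That is a separate matter, but it is why both appear as yardsticks below.

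**Formula.** Let h be the proportion exclusive in hospital in an arm, y1 and y0 the 2-week exclusivity rates after exclusive and non-exclusive hospital feeding, and m1 and m0 the corresponding loss rates. The rate seen among responders is

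[h(1 - m1)y1 + (1 - h)(1 - m0)y0] / [h(1 - m1) + (1 - h)(1 - m0)].

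This treats every lost woman as wholly absent and uses a simple difference in proportions.

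**Setting A (assumed):** y1 = .60, y0 = .05. For a true rate of .27, h = (.27 - .05)/.55 = .40. For .442, h = (.442 - .05)/.55 = .713. Feeding-dependent loss is 10% v 35%; independent loss is 25%.

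- At a true rate of .27 with dependent loss: (.40 x .90 x .60 + .60 x .65 x .05) / (.36 + .39) = .2355/.75 = .314.
- At a true rate of .442 with dependent loss: (.713 x .90 x .60 + .287 x .65 x .05) / (.641 + .187) = .476.
- With independent loss the true rate is returned.

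| Loss depends on hospital feeding in | True difference | Responders' difference | Bias |
|---|---|---|---|
| both arms equally | 0 | .314 - .314 = .000 | 0 |
| both arms equally | .172 | .476 - .314 = .162 | -.010 |
| AME only | 0 | .314 - .270 = .044 | +.044 |
| control only | 0 | .270 - .314 = -.044 | -.044 |
| AME only | .172 | .476 - .270 = .206 | +.034 |
| control only | .172 | .442 - .314 = .128 | -.044 |

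With lighter loss (5% v 15% where dependent, 10% where independent), equal dependence gives 0 under no effect and -.003 at a true .172. Dependence in AME only gives +.012 to +.015.

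**Setting B (assumed):** no effect, h = .50, y1 = .48, y0 = .06, so the true rate is .27.

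- Loss 10%/40%: (.90 x .48 + .60 x .06)/1.50 = .312.
- Loss 10%/10%: .270. Against .312 the bias is 4.2 points.
- Loss 15%/10%: (.85 x .48 + .90 x .06)/1.75 = .264. Against .312 the bias is 4.8 points.
- Equal loss rates in both arms, for example 10%/20%: zero.

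The sign follows whichever arm has the feeding-dependent loss. As a yardstick, 4.2/21.5 is about a fifth of the .215 rise.

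**Effect of using the record.** In these settings loss depends only on hospital status and arm, so responders within each hospital stratum are representative. Reweighting to all randomised women gives .40 x .60 + .60 x .05 = .27 in Setting A, and the bias is removed.

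**The case against.** The strongest reply has four parts.

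1. **Bias is not inevitable.** A reader might infer that any link between early feeding and survey loss biases the primary contrast. The arithmetic does not support that: equal dependence with no effect gives zero, and equal dependence with a true .172 gives about -1 point. The larger figures need dependence that differs by arm, which no passage reports. The documents make it conceivable, no more: the attention-control text worries about incentive to stay in the study, and daily diaries with reminders are described only for AME.

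2. **The plan has missing-data provisions.** It examines patterns of loss, compares dropouts with completers and allows pattern mixture models. This stands as description. But the comparisons detect dependence without correcting it, and the pattern mixture model is optional, with no patterns or trigger specified.

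3. **The hospital record is not ignored.** A reader might infer that the plan leaves it out altogether. It does not: in-hospital breast milk has its own model. The record is absent only from the 2-week models. It could enter as an optional covariate, but that would not restore a woman with no outcome. Being measured after randomisation, it would also change the treatment contrast.

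4. **Few women may be affected.** A reader might infer that 70 women would be lost. That is a ceiling: the 25% includes intervention dropouts, whom intention-to-treat keeps. Telephone and clinic contact are planned when electronic surveys fail, and women who miss week 2 but answer later stay in the model. All of this stands, and it lowers the likely size.

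**Conclusion.** The concern holds as a limited one. The statement that everyone is included is not met for women with no postpartum survey, and a relevant record that needs no survey is kept out of the 2-week models. The resulting bias is possible, not certain. It runs from zero, through about -1 point, to 4 to 5 points in either direction if dependence differs by arm. These sizes rest on assumed loss rates and assumed links between hospital and 2-week feeding; the documents supply only the .27, the detectable effect, the 280 and the 25%.

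Only exclusivity is sized here. The same mechanism applies to percentage of feedings. For self-efficacy, in-hospital feeding is not a measure of the outcome and could only inform imputation. Nor does the record cure loss driven by feeding difficulties after discharge. The change is worth making because it is cheap and addresses loss that tracks early feeding.

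**What to change.** In the SAP:

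- Multiply impute missing 2-week outcomes for all randomised women, separately by arm, with medical-record in-hospital feeding (any formula yes/no; percentage breast milk) as auxiliary variables. Apply this to all three primary outcomes, recognising that for self-efficacy the record is an auxiliary only.
- State that in-hospital feeding is not an adjusting covariate in the efficacy models, because it is measured after randomisation.
- Pre-specify a not-at-random sensitivity analysis, for example delta-adjusted imputation, to cover loss driven by feeding after discharge.
- Report by arm how many women have no postpartum outcome, and how many of them have a hospital feeding record.

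The cost is SAP wording, one imputation model and a little more analysis; no new data collection is needed. The record will still be missing for births outside the hospital system, and for withdrawn women if access to their records ends at withdrawal, which the available text does not settle.

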The primary outcome variables of interest for the short-term efficacy of the AME intervention at 2 weeks postpartum (Aim 1) are 1) proportion of mothers providing 100% breast milk, 2) percentage of feedings that were breast milk, and 3) breastfeeding self-efficacy. Secondary breastfeeding outcomes for short-term efficacy include proportion of mothers with any breastfeeding, perceived milk supply, onset and days to lactogenesis II, and days to any formula and/or breastfeeding cessation. Secondary long-term efficacy outcomes (Aim 2), which will be assessed at all follow-up points until 12 months postpartum (or breastfeeding cessation/loss to follow-up), are duration of breastfeeding in days and any breastfeeding at postpartum follow-ups; the continuous and categorical type versions of breastfeeding exclusivity; and the proximal intervening outcomes (i.e., mediating variables) including the repeatedly measured breastfeeding self-efficacy and perceived milk supply.

Generalized linear mixed-effects modeling with linear contrasts will be used to examine the effect of treatment assignment (AME vs. attention control) for each repeatedly assessed outcome, with treatment group assignment as the between-subjects factor, time as the within-subjects factor, and an interaction between time and treatment group. Given the level of measurement and observed data distribution of the particular dependent variable, an appropriate error structure and link function to the linear predictors will be assumed. For example, for breastfeeding exclusivity and any breast feeding, each assessed as a binary variable, a binomial error structure will be assumed and a logit link to the predictors will be applied, while for the continuous type versions of breastfeeding exclusivity and the interval-scaled breastfeeding self-efficacy, a normal error

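### The Aim 2 outcome definition ends assessment at breastfeeding cessation, the survey schedule does not, and no rule scores feeding outcomes after cessation

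*Combined protocol and SAP*

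**What the plan says.** - **Outcome definitions (Analysis Strategies for Aims 1 and 2).** The secondary long-term outcomes are duration, any breastfeeding, exclusivity in binary and continuous form, self-efficacy and perceived milk supply, "which will be assessed at all follow-up points until 12 months postpartum (or breastfeeding cessation/loss to follow-up"). One clause covers the whole list.
- **Data Collection and Procedures Unrelated to Intervention Delivery.** Surveys that include feeding practices "will be completed by participants in both groups at weeks 2, 6, and 12 weeks, and 6 and 12 months postpartum". No exception is made for women who have stopped. Interview timing depends on "if they indicate that they discontinued breastfeeding at the 2 week postpartum survey", so the surveys do capture cessation.
- **Analysis set.** Under intent-to-treat, "all participants will be included in analyses as randomized".
- **Preliminary Analyses.** Missing-data patterns will be studied to "identify the possible covert missing data mechanisms, and inform the choice of the strategies to handle missing data". Likelihood methods are offered under the condition "If data are ignorably missing (i.e., not related to the outcome itself"). Otherwise, "we may use pattern mixture modeling to account for informative attrition".
- **Models.** Repeated outcomes go to generalized linear mixed models with contrasts at each time point, participant random effects, and a covariance structure chosen by AIC or BIC. Duration goes to Cox regression.
- **Status of Aim 2 (Sample Size and Power).** "the examination of long-term efficacy of AME is more exploratory (Aim 2").

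**The concern.** The clause gives two different things the same consequence. Loss to follow-up means that the value is unknown. Cessation means that feeding status is largely known: the woman is no longer breastfeeding. For duration, ending at cessation is natural, because cessation is the event. For any breastfeeding, exclusivity and percentage of feeds, it removes the unfavourable values from the later waves.

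If the clause is applied as written, a 6- or 12-month contrast compares, partly or wholly, women still breastfeeding in each arm. AME may itself change who continues, so randomisation no longer protects that comparison. A benefit through longer breastfeeding could be hidden, and a benefit confined to intensity among continuers could be inflated.

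**Working it through.** The plan states no figure on this point and no feeding rates after 2 weeks. **Every rate below is therefore an assumption, used to show direction and rough size.**

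**1. What a literal reading produces.** There are two ways to follow the clause:
- *No record*: nothing is kept from cessation on. Every recorded value of any breastfeeding is then yes, and no contrast is left.
- *One zero*: the wave at which cessation is reported is scored zero, and nothing is kept afterwards.

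**2. Exact arithmetic, percentage of feeds at 12 months.** Let p be the proportion still breastfeeding and m the mean percentage among them. All randomised, with stoppers at 0: pA·mA − pC·mC. Continuers only: mA − mC.

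| Assumed benefit | p, AME v control | m, AME v control | All randomised | Continuers only |
|---|---|---|---|---|
| Longer only | 0.50 v 0.35 | 70 v 70 | 35.0 − 24.5 = +10.5 | 0 |
| Intensity only | 0.50 v 0.50 | 90 v 80 | 45.0 − 40.0 = +5.0 | +10 |
| Intensity only | 0.35 v 0.35 | 80 v 70 | 28.0 − 24.5 = +3.5 | +10 |
| Both | 0.50 v 0.35 | 80 v 70 | 40.0 − 24.5 = +15.5 | +10 |
| More, less intensive continuers | 0.50 v 0.35 | 65 v 70 | 32.5 − 24.5 = +8.0 | −5 |

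Binary exclusivity behaves the same way. With 60% v 45% continuing and 50% v 60% of continuers exclusive, the difference is 0.60×0.50 − 0.45×0.60 = +3.0 points among all randomised, but −10.0 among continuers.

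**3. Does likelihood estimation repair this?** Simulation with five waves, absorbing cessation and no other dropout:
- Proportion still breastfeeding by wave, longer-only and both: AME 0.94/0.86/0.76/0.63/0.50, control 0.90/0.78/0.65/0.50/0.35.
- Intensity-only: 0.90/0.80/0.70/0.60/0.50 in each arm.
- Continuers' percentage: base + λb + N(0, 15²), clipped to 1–100, with b ~ N(0, 1). The base is 70 v 70 (longer only) or 80 v 70 (intensity only, both).
- The log cessation hazard falls by g·b. The pair (g, λ) is (0, 0), (0.5, 8) or (1, 15) for no, moderate and strong links between cessation and intensity.

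The table gives 12-month AME minus control differences for no / moderate / strong link. The no-record column and the first one-zero column use a separate unstructured covariance in each arm. The last column uses a common random intercept, from a smaller run whose true values agreed to about 0.3 point.

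| Benefit | True | No record | One zero, unstructured | One zero, random intercept |
|---|---|---|---|---|
| Longer only | +10.5 / +10.5 / +10.6 | 0.0 / −0.7 / −1.6 | +6.7 / +12.0 / +19.2 | +7.2 / +8.4 / +10.0 |
| Intensity only | +4.8 / +4.6 / +4.1 | +9.5 / +9.2 / +8.7 | +8.1 / +5.5 / +1.7 | +8.0 / +6.9 / +5.4 |
| Both | +15.2 / +15.0 / +14.6 | +9.5 / +8.5 / +7.0 | +14.2 / +17.1 / +20.8 | +13.7 / +14.5 / +15.2 |

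Re-coding the simulation moved no cell by more than 0.8 point. The no-record bias is nearly the same under either covariance form. The one-zero bias is not: the extremes (+19.2, +20.8, +1.7) belong to the unstructured fit, and with a random intercept several cells lie close to the truth.

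**4. Any breastfeeding and the share without a value.** Under one zero, with 63% v 50% still breastfeeding at 6 months and 50% v 35% at 12 months, the recorded 12-month proportions are 0.50/0.63 = 79.4% and 0.35/0.50 = 70.0%. That is +9.4 points against a true +15. These are raw proportions, not the planned logistic mixed-model contrast. Women with no 12-month value: (0.50 + 0.65)/2 = 57.5% under no record, and (0.37 + 0.50)/2 = 43.5% under one zero.

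**The case against.** The strongest reply is that nobody would run the analysis this way. No record would empty the any-breastfeeding outcome, which the plan lists and models as binary. Everyone is surveyed to 12 months and analysed as randomised, and the clause sits naturally with duration, self-efficacy and perceived supply. This largely stands: no record is the less credible reading, and scoring stoppers as not breastfeeding is a plausible intent. But intent-to-treat says who is analysed, not what value a woman has after cessation, and the only sentence on the subject points the other way.

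A second reply is that the missing-data plan covers it. The plan does examine mechanisms and lets them guide the method, so it would be wrong to say that it ignores the problem. Under one zero, later missingness depends on a zero already recorded, which likelihood methods allow in principle. The difficulty there is extrapolation, since no stopper is observed later. Under no record, missingness depends on the unrecorded outcome itself. The pattern-mixture option is discretionary and framed as attrition, and the planned diagnostic compares women who stayed in the study with those who dropped out. A woman who stops breastfeeding but keeps answering surveys is not a dropout.

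Third, the time-point contrasts are aimed particularly at the short-term primary outcomes. That is so, but they are planned at every time point. Fourth, a scoring rule may stand in the questionnaires, which the protocol cites but which are not part of this document. If so, a cross-reference would settle that part, though the clause would still conflict with it.

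**Conclusion.** The two sections conflict and the scoring rule is absent. Under no record, any breastfeeding loses its contrast, and the 12-month percentage contrast is about 0 to −2 against a true +10.5 (longer breastfeeding) or about +9 against a true +4 to +5 (intensity). Under one zero, the bias may be smaller or larger depending on the covariance structure selected, and is sometimes negligible. All of this rests on assumed rates.

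A reader might infer more than the documents support:
- *That the primary result is compromised.* The clause governs Aim 2 only, so it does not cut the 2-week primary contrasts. Cox duration is also unaffected if cessation is the event, as the plan implies.
- *That the bias favours AME.* It can go either way.
- *That the sponsor will drop women who stop.* The text permits that but does not establish it.

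What is affected is a set of secondary outcomes that the plan itself calls more exploratory. The point merits correction before analysis, not alarm.

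**What to change.** Reconcile the outcome definition with the survey schedule:
- Only loss to follow-up ends assessment of any breastfeeding, exclusivity and percentage of breast-milk feeds.
- At each later wave, use the value reported in the survey. Where a woman has reported cessation and reports no later breast-milk feeding or resumption, score no, no and 0. An automatic zero would be unsafe, because stored milk may still be fed after breastfeeding stops.
- Treat only true loss to follow-up as missing under Preliminary Analyses.
- Self-efficacy and perceived milk supply have no natural value after cessation, so label any continuers-only comparison of them as descriptive.

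The cost is one or two SAP sentences and one derivation rule. The surveys are already scheduled, so no new data collection is needed. The downside is many zeros in the percentage outcome, which fit poorly with a normal model. The existing provision for transformations or more robust methods when assumptions are seriously violated can be used for that.
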